## 7.2 Independent Data Monitoring Committee

The IDMC will consist of 2 physicians and 1 statistician who are all external to Seattle Genetics, Inc. and free of any direct involvement with the conduct of this study beyond participation in the IDMC. The primary role of this IDMC will be to monitor safety data during the Phase 2 Portion of this study.

Details of the safety reviews will be provided in the IDMC charter.

## 8.0 Data Review

### 8.1 Data Handling and Transfer

Data handling and transfer specifications will be stated and conducted according to the Data Management Plan (DMP).

### 8.2 Data Screening

Beyond the data review and cleaning built into the PRA DMP, the PRA programming of analysis datasets, and TFLs provides additional data review.

Review of a TFL dry run on the nearly finalized database will allow for further data review prior to finalization. The dry run TFLs will be discussed with the sponsor in a data review meeting to identify any final data issues and seek corrections prior to database lock. The PRA statistician and the sponsor must approve database lock.

## 9.0 Statistical Methods

There are two phases to this study. The primary objective of the Phase 1 Portion of the study is to determine the recommended vadastuximab talirine dose in combination with azacitidine. All analyses in the Phase 1 Portion of the study will be descriptive. There will be no formal inferential analyses performed for the Phase 1 Portion of the study.

The Phase 2 Portion of the study will use inferential statistics to explore the efficacy of vadastuximab talirine dose in combination with azacitidine. All inferential analyses will compare the effect of vadastuximab talirine dose in combination with azacitidine to placebo in combination with azacitidine. Hypotheses will be two sided in nature and will be performed at the  $\alpha = 0.1$  level. Inferential statistics for continuous variables will include the estimate, the standard error (SE) of the estimate, and a 90% confidence interval. Estimates will be presented to 1 decimal more than original data. SE will be presented to 2 decimals more than original data.

Descriptive statistics (mean, median, standard deviations, minimum and maximum values) for continuous variables will be presented. Mean and median will be presented to 1 decimal more than original data. Standard deviation (SD) will be presented to 2 decimals more than original data. Minimum and maximum will match the decimal points in the original data. For categorical variables, summary measures will include the frequency and percentage (with 1 decimal place) of subjects in each category.

All data summaries and tabulations will be presented by dose level using the Safety set for the Phase 1 Portion of the analysis, and by treatment group for the ITT evaluable set for the Phase 2 Portion of the analysis set unless otherwise noted. For efficacy and exploratory analyses, further subgroup analyses are not planned.

All data summaries and tabulations will be prepared with SAS Version 9.1.4 or higher.

### 9.1 Subject Disposition

An accounting of study subject disposition will be tabulated by dose level and total, and the number of subjects in each analysis set will be summarized, i.e. all safety set and DLT-evaluable set for the Phase 1 Portion of the study. A similar analysis by treatment arm and total will be summarized for the ITT set, safety set, and efficacy evaluable set for the Phase 2 Portion of the study.

A tabulation of the number and percentage of subjects enrolled in the study (as defined by answering Yes to the eCRF question of “Will the patient be enrolled into the study?”) at each site will be summarized by dose level and total for the Phase 1 and 2 Portion of the study.

Subjects who discontinue study treatment and subjects who withdraw from the study will be summarized by treatment arm and total along with reasons for discontinuation or withdrawal, along with number of subjects who are currently on study and on treatment. A summary table of follow up will be generated for the time from first dose to the time of last assessment, the time from end of treatment to the time of last assessment and the time from end of treatment to end of study. The summary will be presented for all enrolled subjects for the Phase 1 Portion summary and for the ITT set for the Phase 2 Portion.

A listing of subjects of the safety set for the Phase 1 Portion of the study and the ITT set for the Phase 2 Portion of the study who discontinued from the study and discontinued from the treatment will be presented including subjects’ identifier, treatment center, the specific reason for discontinuation and/or for discontinuation of study treatment, the date of the last dose and the duration of treatment before discontinuation. A listing of subject eligibility and a listing of subject analysis sets will also be provided.

## 9.2 Protocol Deviations and Violations

Important protocol deviations (defined as protocol violations by Seattle Genetics) are those that represent a divergence from the protocol that could have a significant effect on the integrity of the study data, or on the subject's rights, safety, or welfare. Important protocol deviations also include exemptions to the study inclusion/exclusion criteria and will be summarized by category, treatment arm and/or dose level and total, and study portion. A listing of subjects with important protocol deviations will be presented.

## 9.3 Treatments

### 9.3.1 Extent of Study Drug Exposure

#### Phase 1 Portion Exposure

During the Phase 1 Portion of the study vadastuximab talirine will be administered every 4 weeks (after azacitidine on the last day of azacitidine administration) via IV at the assigned dose level (3 to 20 mcg/kg), based on the dose evaluation cohort.

Subjects will also receive azacitidine 75 mg/m^2 SC or IV (at the investigator's discretion) for 7 days (7 consecutive days or 5 days on/2 days off/2 days on), beginning on Day 1 of repeated 4-week cycles.

#### Phase 2 Portion Exposure

During the Phase 2 Portion of the study, subjects will be randomized to receive either vadastuximab talirine administered every 4 weeks (after azacitidine on the last day of azacitidine administration) via IV push at the dose determined in the Phase 1 Portion or placebo every 4 weeks (after azacitidine on the last day of azacitidine administration) via IV push.

All subjects will also receive azacitidine 75 mg/m^2 SC or IV (at the investigator's discretion) for 7 days (7 consecutive days or 5 days on/2 days off/2 days on), beginning on Day 1 of repeated 4-week cycles.

Treatment administration of both vadastuximab talirine and azacitidine will be summarized for both study phases by dose level using the safety set. The number and percentage of subjects whose dose was ever modified will be summarized by modification type, cycle and overall (i.e. over all drug administrations for a subject). Summary statistics related to duration of treatment and compliance will be presented as detailed below. For the continuous parameters, the mean, SD, median, minimum and maximum will be presented. The following summary statistics related to drug exposure will be calculated by dose level:

The number and percentage of subjects with at least 1 dose delayed, the number of doses delayed, at least 1 dose reduced, the number of doses reduced, the number of subjects with at least 1 dose unplanned adjustment and reasons for unplanned adjustment, and number of unplanned dose adjustments, the number of subjects with at least one infusion-related reaction, the number of infusion-related reactions, the number of subjects with a delayed hypersensitivity reaction, the number of delayed hypersensitivity reactions, the duration of treatment (weeks), the

number of doses received, the number of treatment cycles received (continuous summary), the number of subjects receiving 1, 2, 3, etc. cycles, the cumulative dose administered ( $\mu\text{g}/\text{kg}$  and total  $\mu\text{g}$ ), the average dose per cycle ( $\mu\text{g}/\text{kg}$  and  $\mu\text{g}$ ), absolute dose intensity ( $\mu\text{g}/\text{kg}$ ), and relative dose intensity (%) will be presented.

A listing of intended dose regimen, intended dose, actual dose administered, and reasons for dose delayed, dose reduced, dose adjustment, and/or infusion-related reactions will be displayed.

### 9.3.2 Concomitant Medications

Other than the study drugs, any medication taken by subjects during the course of the study with a start date on or after the first dose of any study drug, start date prior to first dose date and end date after first dose date or marked as ongoing, will be considered concomitant. Medications stopped prior to the date of the first dose of any study drug will not be considered concomitant. Prior medications include all medications with a start date before the first day of treatment of any study drug and stopped prior to the date of first dose. Subjects in the safety set with multiple uses of a concomitant medication will be counted once for a given Anatomical-Therapeutic Chemical (ATC) and preferred name.

The number and percentage of subjects with each concomitant medication will be summarized by ATC class and preferred name for all treated subjects by planned dose level for each study portion. Preferred names will be presented in descending order of frequency in total.

Additionally, all medications will be listed by subject, displaying verbatim name, synonym (if applicable) and preferred name, indication, and start and stop dates.

### 9.4 Demographic and Baseline Characteristics

The number and percentage of subjects will be provided for Sex (male, female), race (American Indian or Alaska Native, Asian, Black or African American, Native Hawaiian or Other Pacific Islander, White, Other), ethnicity (Hispanic or Latino, Not Hispanic or Latino), ECOG performance status stratification category (0, 1 or 2), and IPSS stratification category (intermediate-2, high risk). Descriptive statistics will be provided for age (years), weight (kg), height (cm), and body surface area (BSA).

Baseline disease characteristics will be presented. The number and percentage of subjects will be provided for MDS Subtype (WHO 2008 Classification), cytopenias (hemoglobin count  $< 10$  g/dL, absolute neutrophil count  $< 1500/\mu\text{L}$ , platelet count  $< 100,000/\mu\text{L}$ ), blasts in the bone marrow (5-10%, 11-20%), cytogenetics (normal, all other abnormalities not valued as good or poor, 3 or more abnormalities or abnormal chromosome 7), IPSS classification (low, intermediate-1, intermediate-2, high), cytogenic category (very good, good, intermediate, poor, very poor), and IPSS-R category (very low, low, intermediate, high, very high) at baseline. Descriptive statistics will be provided for IPSS-R score, time since initial diagnosis, hemoglobin (g/dL), absolute neutrophil count ( $\times 10^9/\text{L}$ ), platelets ( $\times 10^9/\text{L}$ ), and bone marrow blasts (percent).

Prior cancer-related therapy data will be summarized as number and percentage for each therapy type (systemic therapy, radiotherapy) and current disease status of prior cancer (complete

remission, stable disease, active disease). In addition, the number and percentage of subjects with any prior therapy will be displayed.

Medical history will be summarized by count and percentage of subjects experiencing medical history events by Medical Dictionary for Regulatory Activities (MedDRA) system organ class (SOC) and preferred term (PT).

Summaries will be presented by treatment group and study phase. Summaries for the Phase 1 Portion will be presented using the Safety Set. Summaries for the Phase 2 Portion will be presented using the ITT set.

By-subject listings include demographic and baseline characteristics, initial disease diagnosis, prior cancer-related therapy, and general medical history.

## 9.5 Efficacy Analyses

The primary endpoint of the Phase 2 Portion is ORR, and the study will be unblinded for analysis of ORR after all subjects have completed 6 cycles of therapy or have discontinued treatment for any reason before completing 6 cycles. Data collection for the secondary efficacy endpoints and the safety and other endpoints will continue in an unblinded or partially blinded fashion until all subjects have discontinued study treatment.

Primary and secondary endpoint analyses will be presented for the ITT set and the All Treated set for the Phase 2 Portion of the study. Summaries for the Phase 1 Portion of the study will be presented for the safety set.

### 9.5.1 Primary Efficacy Endpoint

Subjects will be assigned a response status based on assessments at each visit. The primary efficacy endpoint of the Phase 2 Portion of the study is ORR, defined as the proportion of subjects who achieve any category of CR (CR and Marrow CR) or PR based on the 2006 IWG criteria for MDS that are summarized in Appendix 18.6 of the protocol. ORR will be assessed during the on treatment period until EOT. Subjects who are not evaluable at any time during the treatment period will be considered non-responders.

The ORR will be summarized by treatment group and the treatment difference in ORR will be tested using a Cochran-Mantel-Haenszel (CMH) test stratified by randomization strata (ECOG status at baseline, that is, 0 vs 1 or 2 and IPSS category at baseline, that is, Intermediate-2 vs High risk). The 90% confidence interval for the treatment difference in ORR will be calculated.

ORR will be summarized descriptively, including 95% confidence intervals using the exact binomial method, by dose for the Safety set in the Phase 1 Portion of the study.

### 9.5.2 Secondary Efficacy Endpoints

The following analyses for the secondary endpoints will be performed for the Safety set for the Phase 1 Portion and ITT and EE set for the Phase 2 Portion of the study, respectively.

CR Rate, HI rate, and Rate of transformation to AML will be summarized descriptively by treatment arm or dose level. The corresponding 90% confidence intervals for the difference in rate between the 2 treatment arms will be provided for the 2 Portion of the study.

The number and percent of subjects with disease response of CR, Marrow CR, PR, stable disease [SD], PD or Relapse from CR / PR as collected on the Response Assessment CRF form will be presented at each visit by treatment arm or dose level.

Time-to-event variables (DOR, PFS, and OS) will be summarized descriptively using the Kaplan-Meier methodology using the SAS LIFETEST procedure. Medians and quartiles and their two sided 90% CI using the complementary log-log transformation method will be calculated, where possible. PFS probability at 3, 6, 9, ...51 months with corresponding CIs will be reported. . Kaplan-Meier figures will be presented by treatment arm or dose level.

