Subjects will be stratified by baseline ECOG performance score (0 vs 1 or 2) and IPSS risk category (Intermediate-2 vs High risk).

Sample Size Considerations

Phase 1 Portion (minimum of 6 subjects per cohort): Six subjects are adequate to appropriately assess the safety profiles and DLT rates of differing dose levels of vadastuximab talirine in combination with azacitidine. If the true incidence rate of DLT is 10%, the probability of considering a dose level tolerable (ie, ≤ 1 of 6 subjects experiences a DLT) will be 88.6%. If the true incidence rate of DLT is 50%, the probability of considering a dose level tolerable will be 10.9%.

Phase 2 Portion (106 subjects): A sample size of 106 subjects will provide 85% power to detect a treatment difference in ORR, assuming an ORR of 30% for azacitidine alone vs 55% for the combination of vadastuximab talirine with azacitidine, at a 2-sided 0.1 alpha level.

Analysis Methods

The primary efficacy endpoint of the study is ORR in the Phase 2 Portion, defined as the proportion of subjects who achieve any category of CR (CR and Marrow CR) or PR based on the 2006 IWG criteria for MDS. Subjects who receive other MDS therapies before a response has been observed will be considered non-responders. The ORR will be summarized by treatment group and the corresponding 90% confidence intervals will be calculated. The treatment difference in ORR will be tested using a Cochran-Mantel-Haenszel test.

Secondary efficacy endpoints include CR rate, HI rate, DOR, PFS, rate of transformation to AML, and OS. Treatment differences in the rate of CR, HI, and transformation to AML will be analyzed by the same method as for ORR. DOR, PFS, and OS will be estimated with the Kaplan-Meier method and tested with the stratified log-rank test.

The primary analysis of efficacy will be based on the intent-to-treat (ITT) analysis set, which includes all subjects who are randomized in the Phase 2 Portion of the study.

Descriptive summaries of subject disposition, demographics, disease characteristics, baseline and pharmacodynamics biomarkers, extent of exposure to study treatment, and safety will be provided. The relationship of vadastuximab talirine PK and relevant pharmacodynamic endpoints, safety, or efficacy may be explored; these analyses, if conducted, will be descriptive.

DATE AND VERSION: 13 April 2017, Version 03

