13.6.4.2 Secondary Efficacy Endpoints

Time-to-event variables (DOR, PFS, and OS) will be summarized descriptively using the Kaplan-Meier estimate. Additional details will be provided in the SAP. Secondary endpoints will be assessed in the ITT population (except as indicated below).

CR Rate: Response (CR/Marrow CR, PR, ORR [CR/Marrow CR+PR], HI rate, stable disease [SD], and PD) will be summarized descriptively by treatment arm. CR rate will be summarized with 90% confidence intervals. Rate of transformation to AML will also be summarized.

DOR (for PR/CR and CR): DOR is defined as the time from first observation of response (PR+CR/Marrow CR or CR/Marrow CR) to disease progression/relapse or death from any cause, whichever occurs first. Durations will be assessed in the ITT population with a PR or CR and calculated separately for subjects with CR/Marrow CR and those with PR+CR/Marrow CR combined. For subjects with a remission without subsequent disease progression/relapse or death on study, DOR will be censored at the time of the last disease assessment demonstrating a lack of disease progression/relapse. Subjects who receive another anti-neoplastic therapy in the absence of documented progression will be censored at the time of receiving off-protocol therapy for

malignancy, EXCEPT that subjects who receive stem cell transplant in remission will continue to be followed for progression.

Progression-free Survival: PFS is defined as the time from first dose of study medication to first documentation of disease progression/relapse, or to death due to any cause, whichever occurs first. For subjects without disease progression/relapse or death on study, PFS will be censored at the time of the last on-study disease assessment demonstrating a lack of disease progression/relapse. If more than one date of progression is available, the earliest date will be used to determine PFS. Subjects who receive another anti-neoplastic therapy in the absence of documented progression will be censored at the time of receiving off-protocol therapy for malignancy, EXCEPT that subjects who receive stem cell transplant in remission will continue to be followed for progression.

Overall Survival: OS is defined as the time from first dose of study medication to death due to any cause. For subjects not known to have died at the end of the study, OS will be censored at the time the subject was last known to be alive (including follow-up data).

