### 1.1 Changes from Protocol

Disposition will be presented by dose level and total, and will not be presented by cycles. The summary of duration of treatment gives information on cycles received, so disposition by cycles is not needed. Hematologic improvement was not able to be calculated as the required data components were not captured in the data.

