### Secondary Objectives:

- To evaluate the safety of the combination of vadastuximab talirine and azacitidine (Phase 1 and Phase 2 Portions)
- To compare the CR rate between treatment arms (Phase 2 Portion)
- To compare the hematologic improvement (HI) rate between treatment arms (Phase 2 Portion)
- To compare the duration of response (DOR) between treatment arms (Phase 2 Portion)
- To compare progression-free survival (PFS) between treatment arms (Phase 2 Portion)
- To compare the rate of transformation to acute myeloid leukemia (AML) between treatment arms (Phase 2 Portion)

- To compare the overall survival (OS) between treatment arms (Phase 2 Portion)

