## 6.0 Analysis Sets

### 6.1 Intent-to-Treat Set

The intent-to-treat (ITT) set will include all subjects who are randomized in the Phase 2 Portion of the study. This set will be used for baseline and efficacy analyses. If the randomized treatment arm differs from the actual treatment at any drug administered periods for a given subject, that subject will be analyzed according to the randomized treatment arm.

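### PFS, OS and DOR: the protocol synopsis plans a stratified log-rank test, protocol 13.6.4.2 and SAP 9.5.2 are descriptive only, and the objectives to compare arms are left without a contrast

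*SAP*

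**What the plan says.** The protocol describes the analysis of the time-to-event endpoints twice. Under Analysis Methods in the synopsis: "DOR, PFS, and OS will be estimated with the Kaplan-Meier method and tested with the stratified log-rank test". In section 13.6.4.2: "Time-to-event variables (DOR, PFS, and OS) will be summarized descriptively using the Kaplan-Meier estimate", with further detail left to the SAP.

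SAP 9.5.2 states: "Time-to-event variables (DOR, PFS, and OS) will be summarized descriptively using the Kaplan-Meier methodology using the SAS LIFETEST procedure". The planned outputs are medians and quartiles with two-sided 90% CIs, PFS probabilities at three-month steps, and Kaplan-Meier figures by arm or dose level.

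The SAP 2.0 objectives remain comparative. For PFS the objective reads "To compare progression-free survival (PFS) between treatment arms (Phase 2 Portion", and DOR and OS have parallel wording.

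SAP 1.1, which lists changes from the protocol, has two entries. One concerns disposition ("Disposition will be presented by dose level and total, and will not be presented by cycles"). The other says that hematologic improvement could not be calculated.

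For the binary secondary endpoints the synopsis says: "Treatment differences in the rate of CR, HI, and transformation to AML will be analyzed by the same method as for ORR". SAP 9.5.2 gives descriptive rates, and "90% confidence intervals for the difference in rate between the 2 treatment arms will be provided".

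**The concern.** A randomized, placebo-controlled portion with objectives to compare PFS, OS and DOR needs a stated contrast for each. The SAP was the place to settle the protocol's two versions. It adopted the descriptive one, left the comparative objectives standing and recorded nothing.

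Timing adds to this. SAP 9.5 unblinds the study for ORR once all subjects have completed six cycles or stopped treatment earlier, and secondary data collection then continues unblinded or partially blinded. If no contrast is fixed beforehand, any later choice of test, strata, analysis set or time origin for PFS and OS could be made with treatment assignments known.

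**Working it through.** **1. The plan's own sizing figure.** Inputs from SAP 3.2 and 3.4: 106 subjects randomized 1:1 (53 per arm), ORR 30% vs 55%, two-sided alpha 0.1, stated power 85%.
- Unpooled: SE = √[(0.30×0.70 + 0.55×0.45)/53] = 0.0929; power = Φ(0.25/0.0929 − 1.645) = 85.2%.
- Pooled variance under the null: 83.9%.

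The stated power reproduces, and it concerns ORR only. Neither document gives an event count, hazard ratio or power for PFS, OS or DOR.

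**2. The passages side by side (DOR, PFS, OS).**
- Protocol synopsis: Kaplan-Meier plus stratified log-rank test.
- Protocol 13.6.4.2: descriptive Kaplan-Meier; details left to the SAP.
- SAP 9.5.2: descriptive Kaplan-Meier, by arm.
- SAP 2.0: objectives to compare.
- SAP 1.1: silent.

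**3. Is a contrast supplied elsewhere in the SAP?**
- SAP 9.0 says Phase 2 uses inference at the two-sided 0.1 level but assigns no test to these endpoints.
- SAP 4.4 applies the stratification factors to the primary analysis.
- SAP 9.5.2.1 to 9.5.2.3 and Table 2 give definitions and censoring rules.

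None of these names a log-rank test, a hazard ratio or a between-arm difference for DOR, PFS or OS.

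**4. What a hazard ratio would deliver.** The event counts d are assumptions. With 1:1 allocation, SE(log HR) = 2/√d, and the 90% CI is the estimate divided and multiplied by exp(1.645 × SE).
- d = 40: SE 0.316, factor 1.68.
- d = 60: SE 0.258, factor 1.53.
- d = 80: SE 0.224, factor 1.44.

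Power at two-sided 0.1 is Φ(√d/2 × |ln HR| − 1.645). At 40, 60 and 80 events this gives 49%, 63% and 74% for a true HR of 0.6, and 30%, 40% and 48% for 0.7.

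**5. Time origin.**
- SAP 6.1: "The intent-to-treat (ITT) set will include all subjects who are randomized in the Phase 2 Portion of the study". PFS and OS (SAP 9.5.2.2 and 9.5.2.3) start at first dose, so a randomized, undosed subject has no time zero. Table 2 does not help, because it censors subjects without assessments at the first-dose date.
- A treated-subject analysis is planned alongside ITT. SAP 9.5.2 calls it EE and SAP 9.5 calls it All Treated. SAP 6.0 defines neither label, but both appear to mean the mITT set of SAP 6.4. Everyone in that set has a first-dose date.
- For dosed subjects, Protocol Table 4 (footnote a) puts randomization within one business day before Cycle 1 Day 1. Over a weekend that is about 3 days: 3/30.4375 = 0.10 month, against the median OS of 21 to 24 months cited for azacitidine in Protocol 7.3. Protocol 9.5.5 and 10.1 tie the window to the planned start, so a delayed first dose could lengthen it.

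**The case against.** The strongest reply is that the SAP did as it was told. Protocol 13.6.4.2 is the detailed statistical section; it says descriptive and defers to the SAP. The trial is sized for ORR alone, so descriptive survival summaries are a defensible Phase 2 choice. Neither protocol passage ever planned a hazard ratio or Cox model. Power would also be modest: an observed HR of 0.7 has an upper 90% limit of 1.18, 1.07 or 1.01 at 40, 60 or 80 events (0.7 × 1.68, 1.53, 1.44), so the interval includes 1 each time.

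Most of this stands. The contradiction originates in the protocol, the hazard ratio is an addition, and the results would be supportive. What does not stand is leaving the objectives comparative while specifying no comparison and recording no change. That LIFETEST can produce a log-rank test does not pre-specify one.

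A reader might infer three stronger points that the documents do not support:
- That the SAP plainly departs from the protocol. It departs from the synopsis and agrees with 13.6.4.2.
- That the first-dose origin undermines the PFS and OS analyses. It is the protocol's own definition, and the gap touches only undosed subjects in one of two planned sets.
- That arms will be judged by whether their per-arm CIs overlap, at some distorted error level. No passage proposes that rule.

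**Conclusion.** The point holds and should be fixed. Three secondary endpoints (PFS, OS and DOR) have objectives to compare arms but no between-arm test or effect estimate in the SAP, and the protocol disagrees with itself on whether one was intended. CR and AML transformation are better placed: they keep a 90% CI for the difference and lose only the Cochran-Mantel-Haenszel test that the synopsis implies.

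The consequence is limited. The primary ORR test in SAP 9.5.1 and the sample size are unaffected. SAP 9.5.5 makes no multiplicity adjustment, so any secondary p-value would be nominal. The precision figures rest on assumed event counts; the documents supply none. The time-origin gap is secondary, and its effect on dosed subjects is negligible if the randomization window is kept.

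**What to change.** Before unblinding, reconcile the synopsis, protocol 13.6.4.2 and SAP 9.5.2:

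- **PFS and OS.** Add to SAP 9.5.2 the synopsis log-rank test, stratified by ECOG (0 vs 1 or 2) and IPSS (Intermediate-2 vs High risk). Add a stratified Cox hazard ratio with 90% CI, identified as a supportive addition. Extend SAP 4.4 so that the strata apply to these analyses, and label the p-values nominal.
- **DOR.** Either add the log-rank test as supportive, since it compares responders only, or record in SAP 1.1 that it is dropped and reword the SAP 2.0 objective as descriptive.
- **CR and AML transformation.** Record in SAP 1.1 that the 90% CI for the difference replaces the Cochran-Mantel-Haenszel test.
- **Time origin.** One option is to use randomization as the origin in the ITT analysis, as SAP 5.0 already does for Phase 2 30-day mortality. That means amending the PFS definition in SAP 5.0, SAP 9.5.2.2, SAP 9.5.2.3 and Table 2 together, saying how undosed subjects are censored, and listing the change in SAP 1.1. The other is to run the contrast in the mITT set and say so, replacing the EE and All Treated labels.

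The cost is SAP wording and a few table programs. The strata and randomization assignments are already held for the primary analysis, so no new data are needed. SAP 1.0 allows amendments before database lock, but making this one before unblinding keeps the choice independent of treatment assignments.
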